6.10.1.2 Safety Analysis Windows

Except for adverse events, for the analysis window, the last day is always 1 day after the last day of exposure to overall study treatment.

The end of overall treatment is defined as the last day of treatment (e.g., discontinued study or entered follow-up period) +1 and the follow-up period for analysis windows begins at last overall treatment + 2 days and onward (Follow-up Study Day 2).

| Analysis | Scheduled | Analysis Windows (Fezolinetant day) | | | |
|-----------|--------------------|-------------------------------------|----------------------|---------------------|-----------------|
| Visits | Day in Protocol | a) | b) | c) | d) |
| Baseline | Day 1 | Last non-missin | ng value on or prior | to fezolinetant day | y 1 (inclusive) |
| Week 2 | Day 15 | 2 to 22 | | | |
| Week 4 | Day 29 | 23 to 43 | 2 to 43 | 2 to 57 | |
| Week 8 | Day 57 | 44 to 71 | 44 to 71 | | |
| Week 12* | Day 85 | 72 to 92 | 72 to 99 | 58 to 99 | 2 to 127 |
| Week 14 | D99 | 93 to 106 | | | |
| Week 16 | D113 | 100 to 127 | 100 to 127 | 100 to 127 | |
| Week 20 | D141 | 128 to 155 | 128 to 155 | 128 to 155 | |
| Week 24 | D169 | 156 to 183 | 156 to 183 | 156 to 183 | 128 to 267 |
| Week 28 | D197 | 184 to 211 | 184 to 211 | 184 to 211 | |
| Week 32 | D225 | 212 to 239 | 212 to 239 | 212 to 239 | |
| Week 36 | D253 | 240 to 267 | 240 to 267 | 240 to 267 | |
| Week 40 | D281 | 268 to 295 | 268 to 295 | 268 to 295 | |
| Week 44 | D309 | 296 to 323 | 296 to 323 | 296 to 323 | |
| Week 48 | D337 | 324 to 351 | 324 to 351 | 324 to 351 | |
| Week 52** | D365 | 352 to 376 | 352 to 376 | 352 to 376 | 268 to 376 |
| Week 55 | D386 | Last non-missin | ng follow-up day | | |

The data summary by visits will be done following the analysis windows specified in the table below:

a) Apply to liver biochemistry and INR testing

- b) Apply to complete Clinical laboratory and urinalysis, Vital signs
- c) Apply to Blood PD/PK sample, including hormones (PD only at Week 55)
- d) C-SSRS

*The analysis window for the Week 12 ECG assessment (Target Day 85) is FDay 2 through FDay 99

**The analysis window for the Week 52 ECG is last non-missing day from FDay 100 to FUD1; The analysis window for the Week 52 bone marker is FDay 2 to FUD1; The analysis window for the Week 52 TVU and biopsy assessments is FDay 2 until last treatment + 30 days.

If more than one observation exists within the analysis window, the same rules will be followed as described above for efficacy analysis visit windows, except that if there are two observations that have the same distance from the scheduled day, the value that is after the scheduled day will be selected in the analysis.

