12.4 Liver Safety Monitoring and Assessment

Any subject enrolled in a clinical study with active drug therapy and reveals an increase of serum aminotransferases (AT) to $> 3 \times \text{ULN}$ or bilirubin $> 2 \times \text{ULN}$ should undergo detailed testing for liver enzymes (including at least ALT, AST, ALP and TBL). Testing should be repeated within 72 hours of notification of the test results. For studies for which a central laboratory is used, alerts will be generated by the central laboratory regarding moderate and severe liver abnormality to inform the investigator and study team. Subjects should be asked if they have any symptoms suggestive of hepatobiliary dysfunction.

Definition of Liver Abnormalities

Confirmed abnormalities will be characterized as moderate and severe where ULN:

	ALT or AST		TBL
Moderate	$> 3 \times \text{ULN}$	or	$> 2 \times \text{ULN}$
Severe	$> 3 \times \text{ULN}$	and	$> 2 \times \text{ULN}$

In addition, the subject should be considered to have severe hepatic test abnormalities for any of the following:

- ALT or AST $> 8 \times \text{ULN}$
- ALT or AST $> 5 \times \text{ULN}$ for more than 2 weeks
- ALT or AST $> 3 \times \text{ULN}$ **AND** TBL $> 2 \times \text{ULN}$ or INR > 1.5 , or
- ALT or AST $> 3 \times \text{ULN}$ with the appearance of fatigue, nausea, vomiting, right upper quadrant pain or tenderness, fever, rash and/or eosinophilia ($> 5\%$ increase above baseline)

The investigator may determine that abnormal liver test results, other than as described above, may qualify as moderate or severe abnormalities and require additional monitoring and follow-up.

Follow-up Procedures

Confirmed moderate and severe abnormalities in hepatic tests should be thoroughly characterized by obtaining appropriate expert consultations, detailed pertinent history, physical examination and laboratory tests. The site staff is to complete the liver abnormality case report form (LA-CRF). Subjects with confirmed liver aminotransferases (ALT or AST) elevations should be followed as described below.

Moderate liver test abnormalities as defined above should be repeated 2 to 3 times weekly, and then weekly or less if abnormalities stabilize or the study drug has been discontinued and the subject is asymptomatic.

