| Target day | Analysis window | Analysis visit |
|------------|---|----------------|
| D1 | last non-missing value on or prior to day 1 | Baseline |
| D29 | FD22 to FD36 | Week 4 |
| D85 | FD72 to FD 92 | Week 12 |
| D113 | FD106 to FD120 | Week 16 |
| D141 | FD134 to FD148 | Week 20 |
| D169 | FD162 to FD176 | Week 24 |
| D197 | FD190 to FD204 | Week 28 |
| D225 | FD218 to FD232 | Week 32 |
| D253 | FD246 to FD 260 | Week 36 |
| D281 | FD274 to FD288 | Week 40 |
| D309 | FD302 to FD316 | Week 44 |
| D337 | FD330 to FD344 | Week 48 |
| D365 | FD358 to FD372 | Week 52 |

The VMS efficacy windows are smaller because they are calculated from daily data and are not dependent on the scheduling of visits. The non-VMS efficacy endpoint are not collected during the follow-up period.

If more than one observation exists within the analysis window, the observation closest to the scheduled visit day will be selected for that visit. If there are two observations that have the same distance from the scheduled day, the value that is before the scheduled day will be selected in the analysis. If more than one observation is made on the same day, an average value if continuous, or the worst value if categorical, will be included in the analysis.

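### 52-week SAP 6.10.1.2: the Week 14 and Week 16 liver/INR windows overlap on fezolinetant days 100 to 106, and no rule assigns a sample there to one visit

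*SAP*

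**What the plan says.** The 52-week SAP, 6.10.1.2, allocates safety samples to analysis visits by fezolinetant day, with separate columns for different assessments. The footnote to column a) reads "Apply to liver biochemistry and INR testing". Column b) covers the full clinical laboratory panel, urinalysis and vital signs. Column c) covers PK/PD samples.

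Week 14 has a window in column a) only: "Week 14 | D99 | 93 to 106". This matches the protocol's Schedule of Assessments, where visit 5b (Week 14) takes only liver biochemistry and INR. Week 16 has the same bounds in all three columns: "Week 16 | D113 | 100 to 127 | 100 to 127 | 100 to 127". The Week 12 row does differ by column: "72 to 92 | 72 to 99 | 58 to 99".

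For several samples in one window, 6.10.1.2 says "If more than one observation exists within the analysis window, the same rules will be followed" as for efficacy. The efficacy rule in 6.10.1.1 is that "the observation closest to the scheduled visit day will be selected for that visit". For safety data a tie goes to the later sample. Neither section deals with a sample that falls in two windows.

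**The concern.** Analysis windows are meant to send each sample to one visit. Here a sample on FD100 to 106 is eligible for two, and the choice within each window is made without reference to the other. A programmer following the text would let one sample fill both rows, or let a sample taken a week or more before Day 113 stand as the Week 16 result.

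The outputs exposed are the by-visit laboratory summaries in 52-week SAP 6.5.2: descriptive statistics, change from baseline, and percentages below and above the reference range. At Week 16 they could include women who had no liver or INR measurement near that visit.

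A gap at Week 16 is plausible. Women miss visits. Protocol 2.2.1 also allows local-laboratory safety tests during COVID-19 site closures, while the quantitative by-visit summaries in 6.5.2 use values evaluated centrally. A locally tested Week 16 could leave an earlier central sample to fill the row.

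**Working it through.** **Inputs.** Target days and window bounds are from 52-week SAP 6.10.1.2, column a). The selection rule is from 6.10.1.1 and 6.10.1.2 (closest to target, tie to the later sample). The visit window of ±3 days is from the protocol's Schedule of Assessments. It gives Days 96 to 102 for Week 14 and Days 110 to 116 for Week 16.

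**1. The rule behind the table.** From Week 2 to Week 52, each upper bound in column a) is the midpoint of adjacent target days, and the next lower bound should be that midpoint plus 1.

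| Boundary | Midpoint | Stated upper | Stated next lower | Overlap (days) |
|---|---|---|---|---|
| Week 8 / 12 | (57+85)/2 = 71 | 71 | 72 | 0 |
| Week 12 / 14 | (85+99)/2 = 92 | 92 | 93 | 0 |
| Week 14 / 16 | (99+113)/2 = 106 | 106 | **100** (rule: 107) | 106−100+1 = **7** |
| Week 16 / 20 | (113+141)/2 = 127 | 127 | 128 | 0 |

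All 14 adjacent boundaries in column a) were checked. The Week 16 lower bound is the only one that breaks the rule, and this is the only overlap.

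**2. Where 100 comes from.** Columns b) and c) have no Week 14 visit, so the neighbours are Days 85 and 113: (85+113)/2 = 99, next lower bound 100. That is right for b) and c). In column a) the Week 12 upper bound was shortened from 99 to 92 to make room for Week 14, but the Week 16 lower bound was not moved to match.

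**3. When one sample is used twice.** Take a Week 14 draw on each of Days 96 to 102, with no repeat or with one repeat 1 to 7 days later. The repeat delay is an assumption: protocol 12.4 says only that the repeat comes within 72 hours of notification of the result. Combine each with a Week 16 draw on Days 110 to 116, or none. The counts below are of patterns, not probabilities.

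- Week 16 drawn on Days 110 to 116: 0 of 392 patterns (49 without a repeat, 343 with). Such a draw is at most 3 days from Day 113, and no earlier sample in the set (latest 102+7 = 109) is closer than 4.
- Week 16 missing, no repeat: 3 of 7, the scheduled draw on Day 100, 101 or 102.
- Week 16 missing, one repeat: 6 of 49. The original must be on Days 96 to 98 and the repeat on Days 100 to 102, at least as close to Day 99 as the original. If the original is on Day 99 or later, the repeat cannot win Week 14.

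**4. When a repeat stands as Week 16.** In the same 49 patterns, count repeats landing on FD100 to 106. For originals on Days 96 to 102 the counts are 4+5+6+7+6+5+4 = 37. Each such repeat is nearer Day 113 than the original, so it becomes the Week 16 value. In 6 of the 37 it also takes Week 14 (step 3); in the other 31 the original keeps Week 14.

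**5. A very late Week 16 draw.** A Week 14 draw on Day 102 is 113−102 = 11 days from target. A Week 16 draw on Day 124 ties and wins as the later sample. One on Days 125 to 127 would lose to the Day 102 sample. This lies far outside the ±3-day visit window.

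**6. Placebo-switch groups.** If the first fezolinetant dose is on study Day 85, FD = study day − 84. The Week 24 visit (Day 169) is then FD85 and Week 28 (Day 197) is FD113. With ±3 days, no scheduled visit lands on FD100 to 106, so only an unscheduled sample can.

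**7. With the lower bound at 107.** The overlap is 0 days. No pattern puts one sample at both visits, and no sample on FD100 to 106 can be the Week 16 value.

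**The case against.** The strongest reply is that this hardly matters. The 52-week summaries are descriptive with no statistical comparisons (6.1). The analyses that address liver risk do not use visit windows: the ×ULN categories in 6.5.2.1 take the highest value over the active-dose period, and the shift tables in 6.5.2 take the worst finding during treatment. A Week 16 draw on Days 110 to 116 always prevents the problem. All of this stands and limits the size. None of it supplies an allocation rule or explains why column a) alone departs from the midpoint rule.

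A reader might go further and infer that the duplicated sample is usually a repeat of an abnormal Week 14 result, so that the Week 16 liver summaries are selectively abnormal and inflated. The documents do not support this:

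- Under the closest-to-target rule a repeat usually loses Week 14 to the original draw. The plainer route to double use is a routine late Week 14 draw with no Week 16 draw, and that draw is scheduled whatever the enzyme result.
- Protocol 12.4 says "Moderate liver test abnormalities as defined above should be repeated 2 to 3 times weekly". A woman followed that closely will usually have samples after Day 106, and those take Week 16.
- After a woman stops, 52-week SAP 6.5 admits by-visit data only up to one day after the last dose, apart from follow-up visit data. Most later repeats therefore cannot enter the Week 16 row.

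It does remain true that repeats are taken because a result was abnormal, and that a repeat on FD100 to 106 can stand as the Week 16 value when nothing nearer exists. That is a possible source of distortion, not a demonstrated upward bias.

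**Conclusion.** The overlap is certain from the table: FD100 to 106, seven days, in column a) only, with no rule for assigning a sample there. The likeliest cause is that the bound from columns b) and c) was carried over.

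The consequence is small. It reaches only the Week 16 by-visit liver and INR means, changes from baseline and out-of-range percentages, and only women with no sample nearer Day 113. Three of the seven permitted Week 14 visit days (100, 101, 102) fall in the overlap. Scheduled Week 14 draws are at issue only in the 30 mg => 30 mg and 45 mg => 45 mg groups, but an unscheduled sample on FD100 to 106 in a placebo-switch woman is doubly assigned too.

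The documents give neither the number of women affected nor the direction of any distortion; the number is probably small. The step 3 and 4 counts rest on visits within ±3 days and an assumed repeat delay of 1 to 7 days. The overlap itself rests on no assumption. The conclusion does not extend to the peak-value or worst-finding liver tables.

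**What to change.** In 52-week SAP 6.10.1.2, column a), change the Week 16 window to 107 to 127. Leave columns b) and c) at 100 to 127, where there is no Week 14 visit to accommodate.

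This changes one number in a table and no endpoint, analysis set or model. A woman with no liver or INR sample on FD107 to 127 will then correctly show as missing at Week 16. If the SAP is already final, the correction can be recorded and justified in the clinical study report, as its introduction provides.

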6.5 Analysis of Safety

All analysis of safety will be presented by the four treatment groups, as described in Section 6.1 (General Considerations), for SAF_F, unless specified otherwise. For analyses by visit, the visit windows from Section 6.10.1.2 will be applied, and they are all defined relative to the start of fezolinetant. Except for adverse events and follow-up visit data, only data up to one day after the last dose date will be considered for the analyses.

The baseline value for safety endpoint will be the last non-missing value taken on or prior to first dose of fezolinetant unless otherwise noted.

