6.5.5 Other Safety-Related Assessments

C-SSRS results will be summarized by treatment group and analysis visit based on SAF_F.

Ultrasound results (endometrial thickness) and bone marker results will be summarized for the SAF_F population using mean, standard deviation, minimum, maximum and median by treatment group and visit. The within-subject change will be calculated per visit as the post-baseline measurement minus the baseline measurement and summarized by treatment group and visit. The listing will be based on the complete SAF population, including all placebo data and subjects randomized to placebo who never received fezolinetant, because these data were not included in the double-blind 12-week analysis.

Baseline biopsy will be defined as the non-missing value on or prior to first dose of study drug. Biopsy results will be listed based on the complete SAF population, including all placebo data and subjects randomized to placebo who never received fezolinetant, because biopsy data was not included in the double-blind 12-week analysis. Post-baseline biopsy results for subjects originally randomized to placebo will still be listed.

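### The only C-SSRS summary in the 52-week SAP uses one result per visit window, so some early-discontinuation results are not tabulated and distinct women with any positive result are not counted

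*SAP*

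**What the plan says.** All SAP references are to the 52-week SAP unless stated.

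- **Analysis.** Section 6.5.5 has one sentence on this instrument: "C-SSRS results will be summarized by treatment group and analysis visit based on SAF_F".
- **Windows.** In 6.10.1.2, column d) applies to C-SSRS: FD2-127 for Week 12, FD128-267 for Week 24 ("Week 24 | D169 | 156 to 183 | 156 to 183 | 156 to 183 | 128 to 267") and FD268-376 for Week 52.
- **Several results in one window.** Section 6.10.1.2 says "If more than one observation exists within the analysis window, the same rules will be followed as described above for efficacy analysis visit windows". That rule, in 6.10.1.1, is that "the observation closest to the scheduled visit day will be selected for that visit". For safety data a tie goes to the later value. The worst categorical value is taken only among results from the same day.
- **On-treatment limit.** Apart from adverse events and follow-up data, "only data up to one day after the last dose date will be considered for the analyses" (6.5).
- **Collection.** Protocol Table 1 and 5.4.2 schedule C-SSRS at screening, Day 1, Weeks 12, 24 and 52, and follow-up. The Week 52 column of Table 1 also covers the ED visit, and Protocol 2.2.1 has the end-of-treatment procedures done at discontinuation.
- **Other safety data.** Liver tests use each woman's highest value over the whole active period (6.5.2.1), and laboratory shift tables use the worst finding (6.5.2). For ECG, "The analysis window for the Week 52 ECG is last non-missing day from FDay 100 to FUD1". C-SSRS has no comparable rule.

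**The concern.** A woman who stops early has an extra C-SSRS at the visit where she leaves. If it falls in a window that already holds a scheduled result nearer the target day, the scheduled result represents her and the ED result appears in no row. The discontinuation visit is a poor one to leave out of a suicidality summary.

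A second limit is separate from this. Visit rows do not add up to women: someone positive at two visits appears twice, and someone positive only at an unselected assessment does not appear. The planned tables therefore do not show how many women had any suicidal ideation or behavior after starting fezolinetant.

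The 12-week analysis does not fill the gap. It excludes extension-period data (12-week SAP 1 and 6.10.1), and its own C-SSRS summary is also by visit (12-week SAP 6.5.5).

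**Working it through.** **Reproducing the windows.** The inner limits are midpoints of the scheduled C-SSRS days: (85 + 169)/2 = 127 and (169 + 365)/2 = 267. The upper limit, 376, is taken as stated. Window lengths are 127 - 2 + 1 = 126, 267 - 128 + 1 = 140 and 376 - 268 + 1 = 109 days.

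**Which ED days are displaced.** The selection rule (nearest to target, tie to the later value) was applied to every possible ED day, with the ED result taken no later than last dose + 1 day.

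*Women on fezolinetant from Day 1, visits on FD85 and FD169:*
- FD2-84: sole result in its window, so tabulated.
- FD86-127: loses to Week 12. 127 - 86 + 1 = 42 days.
- FD128-168: no other result yet in the Week 24 window, so tabulated.
- FD170-267: loses to Week 24. 267 - 170 + 1 = 98 days.
- FD268-364: sole result in the Week 52 window, so tabulated.
- Total: 42 + 98 = 140 of the 363 days FD2-364 (39%).
- If the scheduled visits are 3 days early or late: FD89-127 (39) + FD173-267 (95) = 134 of 363 (37%).

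*Women switched from placebo:* the study Week 24 visit falls on FD 169 - 85 + 1 = 85, and Week 52 on FD 365 - 85 + 1 = 281.
- Displaced only on FD86-127: 42 of the 279 days FD2-280 (15%).
- If visits are 3 days off: 39 of 279 (14%).

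These are shares of calendar days, not of women.

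**From days to women.** The documents give neither the timing of late drop-out nor a C-SSRS positivity rate, so this is a scenario for one 150-woman arm on fezolinetant from Day 1.

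| Step | Input | Result |
|---|---|---|
| Leave before Week 12 | 20% (12-week SAP 3): 150 x 0.20 | 30 women, all with ED result tabulated |
| Leave over FD86-364 | 0 to 10%, spread evenly (assumption): 150 x 0 to 150 x 0.10 | 0 to 15 women |
| Late ED days displaced | 140 / (364 - 86 + 1) = 140/279 | 0.502 |
| ED results not selected | 0 to 15 x 0.502 | 0 to 7.5 |
| Share of all ED results | 0/30 to 7.5/(30 + 15) | 0 to 17% |
| Of these, positive | 1% to 5% (assumption): up to 7.5 x 0.01 = 0.08 or 7.5 x 0.05 = 0.38 | 0 to about 0.4 women |

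The scenario assumes that every leaver has one on-treatment ED C-SSRS.

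**The case against.** The strongest reply is that nothing here is an error. Protocol 7.5 names C-SSRS without prescribing a form of table, the 52-week analysis is descriptive throughout, and a by-visit summary contradicts neither document. No suicidality signal prompts more: Protocol 1.4.2 reports no clinically meaningful change in suicide status in phase 2b. Liver injury, by contrast, is an important potential risk (Protocol 1.5), which explains its highest-value table. The ECG rule is not fully protective either, since an ED ECG on FD86-99 also loses to an on-time Week 12 ECG. All of this stands. It makes the point an inexpensive improvement and not a correction.

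Adverse event capture is a real backstop. Protocol 5.2.2 and 5.5.1 take in untoward events and unfavorable symptoms from consent onward. SAP 6.5.1 counts women by preferred term up to 21 days after last dose and makes depression an event of special interest. The cover is partial: for abnormal safety assessments, Protocol 5.5.1.1 relies on the investigator's judgment of clinical significance, and it does not name C-SSRS among its examples.

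Four stronger readings are tempting but are not supported:

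- **Positive women cannot be counted at all.** The data are collected. SAP 6.1 has listings carry data from the first fezolinetant dose, so a C-SSRS listing, though none is named, would allow a hand count. The limit concerns only the tables planned in the SAP text.
- **39% of ED results are lost.** That is a share of days. The plan expects about 20% to leave before Week 12, and their on-treatment ED results are kept.
- **The windows are too wide.** They are midpoints between scheduled assessments, and their width keeps ED results that narrower windows would drop. The gap comes from having no per-woman summary beside the one-result rule.
- **ED results taken 2 or more days after last dose are also lost.** The SAP does say "the follow-up period for analysis windows begins at last overall treatment + 2 days and onward", and the follow-up row reads "Week 55 | D386 | Last non-missin | ng follow-up day", so a later Visit 16 result might replace such a value. That row is broken in the extracted table, its application to C-SSRS is inferred, and the effect cannot be sized. The conclusion does not rest on it.

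**Conclusion.** The point holds as a low-priority improvement. By the stated rules, an on-treatment ED C-SSRS on FD86-127 or FD170-267 (women on fezolinetant from Day 1) or on FD86-127 (switched women) is left out of the only planned summary when the scheduled visits were on time. The planned tables also give no count of distinct women with any post-baseline ideation or behavior.

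The expected size is small: 0 to about 7.5 unselected ED results per 150-woman arm, 0 to 17% of ED results, and 0 to about 0.4 women with a positive unselected result. These figures rest on 0 to 10% late drop-out spread evenly and on 1% to 5% positivity, neither of which the documents give; other timing would change them. The 17% also depends on the plan's 20% early drop-out. What stays uncounted is mainly ideation not reported as an adverse event.

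Confidence is medium, because table and listing formats are left to TLF specifications that were not available and may already include a per-woman table.

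**What to change.** Leave the windows and the by-visit table as they are. Add to 52-week SAP 6.5.5 one descriptive table, by treatment group, of each woman's worst post-baseline C-SSRS category: highest ideation level and any suicidal behavior. Use all assessments after the first fezolinetant dose, including ED and unscheduled ones. Show on-treatment results (to last dose + 1 day) and follow-up results separately, each with the number of assessments per woman.

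The cost is one sentence and one table from data already collected, with no test or alpha involved. The downside is that women assessed more often have more chances to be positive, which is why the number of assessments should stand beside the counts. If the TLF specifications already contain such a table, a cross-reference in 6.5.5 is enough.
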